Official Title: Oxygen Reserve Index (ORi)
Expanded Data Set Validation of
INVSENSOR00025

Date of Protocol: July 14, 2020

NCT Number: NCT04079816

Oxygen Reserve Index (ORi) Expanded Data Set Validation of INVSENSOR00025

Protocol/Test Procedure Title	Oxygen Reserve Index (ORi) Expanded Data Set Validation of INVSENSOR00025
Lead Investigator	

 Masimo Corporation [name]
Other Investigators	

 

 

Expected Start Date	Based on IRB Approval Certification Approval Date
Expected End Date	Based on IRB Approval Certification Expiration Date
IRB	E&I West Coast Board – IRB00007807
Date Submitted To IRB	

Protocol Test Abstract:

The objective of this study is to validate the performance of Oxygen Reserve Index (ORi) as computed by the Masimo device in healthy volunteers. The changes in ORi measurements are compared to changes in PaO2 values obtained from arterial blood samples analyzed by a laboratory CO-oximeter reference instrument.

APPROVALS

Author	Date	Engineering	Date
N/A	N/A	N/A	N/A
Quality Assurance	Date	Manufacturing	Date
N/A	N/A	N/A	N/A

Oxygen Reserve Index (ORi) Expanded Data Set Validation of INVSENSOR00025

STATEMENT OF COMPLIANCE

This document is a protocol for a clinical research study sponsored by Masimo Corporation. The study will be conducted in compliance with all stipulations of this protocol, the conditions of IRB approval, all applicable regulations including 21 CFR Part 50, 21 CFR Part 56, 21 CFR Part 812, ISO-14155, and International Conference on Harmonization E6 Good Clinical Practice (ICH GCP).

The protocol, informed consent form(s), recruitment materials, and all participant materials will be submitted to the Institutional Review Board (IRB) for review and approval. Approval of both the protocol and the consent form must be obtained before any participant is enrolled. Any amendment to the protocol will require review and approval by the IRB before the changes are implemented to the study.

1. PURPOSE

This test procedure describes the method used to validate the performance of Oxygen Reserve Index (ORi) as measured by the Masimo INVSENSOR00025 sensors connected to the Masimo Radical-7 pulse oximeter and Masimo Root monitor in healthy volunteers. The changes in ORi measurements are compared to changes in PaO₂ values obtained from arterial blood samples analyzed by a laboratory CO-oximeter reference instrument.

Outcome Measure:

This study reports ORi sensitivity and concordance of directional changes in ORi to directional changes in PaO₂ from blood samples (in the range of 100 to 200mmHg).

2. BACKGROUND

[figure not shown]
Masimo Corporation develops non-invasive medical technologies. These devices have applications in the operating room, critical care unit, emergency room, emergency transport vehicles, as well as physician's offices.

An invasive blood sample analyzed by a CO-oximeter reference instrument gives the best measure of arterial oxygen concentration as well as other blood solutes, but cannot measure these parameters continuously and requires skin puncture, arterial line placement and subsequent risk of infection, hematoma, and other physiological damage. Masimo SET and Masimo Rainbow technologies allow real-time, non-invasive monitoring of oxygen saturation (and other blood solutes) and has the potential to improve clinical outcomes while reducing the cost of care and risks to both patients and clinicians associated with arterial and venous punctures.

2.1. Technology Background

Pulse oximetry technology is governed by the following principles:

- Oxyhemoglobin (oxygenated blood) and deoxyhemoglobin (non-oxygenated blood) differ in their absorption of red and infrared light (spectrophotometry).
- The amount of arterial blood in tissue changes with arterial pulses (photoplethysmography). Therefore, the amount of light absorbed by the varying quantities of arterial blood changes as well.
- The CO-Oximeter utilizes a sensor with various light-emitting diodes (LEDs) that pass light through the site to a photodiode (detector). See figure below.

1. Light Emitting Diodes (LEDs)
(2+ wavelengths)
2. Detector

Oxygen Reserve Index (ORi) Expanded Data Set Validation of INVSENSOR00025

2.2. Parameter Background

A continuous supply of oxygen is essential for normal cell function. Failure of a patient's oxygen supply to meet metabolic needs is common to all forms of circulatory failure, tissue acidosis, and ultimately mortality. Like all essential commodities for body functions, optimal quantities of oxygen are required. A patient's oxygen status can be largely classified into 3 ranges: Hypoxia (less than normal), Normoxia (normal) and Hyperoxia (more than normal). The three states are typically classified using dissolved oxygen levels in the plasma (PaO_2), instead of arterial hemoglobin oxygen saturation (SaO_2), due to sensitivity of PaO_2 in all three states including hyperoxia (unlike SaO_2). Figure 1.¹ shows the three oxygen states based on PaO_2 values along with the relationship between PaO_2 and SpO_2 (which is a proxy for SaO_2)

[figure not shown]

Figure 1: The oxygen dissociation curve with the three oxygen states

Currently, in order for clinicians to monitor a patient's oxygen status, both continuously and non-invasively, they utilize a pulse oximeter to obtain SpO_2 (a proxy for SaO_2) levels. However, SpO_2 is sensitive in the normoxic and hypoxic regions and largely remains flat in the hyperoxic region (Figure 1) clinicians generally resort to invasive blood draws to obtain PaO_2 values which provide oxygen status within the hyperoxic zone. This method has multiple drawbacks such as intermittent samples to potential delay between time of blood draw to the time when the PaO_2 value is obtained through blood gas machines.

The ORi Parameter may help provide clinicians with a convenient noninvasive method for monitoring oxygenation status in the moderate hyperoxic range, that may be used in conjunction with SpO_2 and reference PaO_2 measurements. While not a direct measurement of PaO_2 , ORi is intended to provide a continuous and non-invasive directional trending index which reflects directional changes in oxygenation. The concordance of directional changes to PaO_2 from blood samples is used to validate the ability of ORi to monitor oxygenation status in the moderate hyperoxic range (in the range of 100 to 200mmHg).

¹ Martin, L. (1999). *All you really need to know to interpret arterial blood gases*, Page 73, Lippincott Williams & Wilkins.

Oxygen Reserve Index (ORi) Expanded Data Set Validation of INVSENSOR00025

2.3 Investigational Study Devices

The investigational devices to be used in this study are the Masimo INVSENSOR00025 rainbow disposable sensor, Masimo Radical-7 Pulse CO-Oximeter, and Masimo Root Patient Monitoring and Connectivity Platform. [REDACTED]

[REDACTED]

Investigational sensor is equivalent to the FDA cleared sensors with regard to intended use on the surface of the skin, the choice of materials, biocompatibility, manufacturing process and risk of exposure to the subject to any energy or light source. They do not pose any additional risk to patients as compared to the FDA cleared sensors.

The Masimo Root Patient Monitoring Platform is an FDA-cleared patient monitoring and connectivity platform that offers rainbow[®] and Masimo SET[®] measurements with other parameters in an integrated platform. With docking capabilities for the Radical-7[®] handheld monitor and multiple networking/connectivity options, Root integrates multiple streams of data into one display monitor. The Masimo Radical-7 pulse oximeter is an FDA-cleared noninvasive monitoring platform featuring Masimo SET Measure-through Motion and Low Perfusion[™] pulse oximetry with the option to measure multiple additional blood constituents and physiologic parameters. [REDACTED]

² D. S. Martin and M. P. W. Grocott III. , Oxygen therapy in anaesthesia: the yin and yang of O2 Br. J. Anaesth. (2013) 111 (6): 867-871 doi:10.1093/bja/aet291

² Habre W1, Peták F2. Perioperative use of oxygen: variabilities across age. Br J Anaesth. 2014 Dec;113 Suppl 2:ii26-ii36. doi: 10.1093/bja/aeu380

**Oxygen Reserve Index (ORi) Expanded Data Set
Validation of INVSENSOR00025**

3. REFERENCE

- Consent To Be A Research Subject Oxygen Reserve Index (ORi) Expanded Data Set Validation of INVSENSOR00025
- Oxygen Reserve Index (ORi) Expanded Data Set Validation of INVSENSOR00025 Case Report Form (CRF)
- Oxygen Reserve Index (ORi) Expanded Data Set Validation of INVSENSOR00025 Healthy Volunteers Needed Advertisement
- Oxygen Reserve Index (ORi) Expanded Data Set Validation of INVSENSOR00025 Recruitment Script
- Health Assessment Questionnaire Health Assessment Questionnaire Oxygen Reserve Index (ORi) Expanded Data Set Validation of INVSENSOR00025
- Confidentiality Agreement
- Volunteer payment form
- Informed Consent Process
- Clinical Study Request Form (CSRF)
- Post Care Instructions

5. STUDY POPULATION

5.1. Inclusion Criteria

- Subject is 18-50 years of age.
- Subject weighs a minimum of 110 lbs and no more than 250 lbs unless subject is over 6 feet tall.
- Hemoglobin value is greater than or equal to 11 g/dL.
- Baseline heart rate ≥ 45 bpm and ≤ 85 bpm.
- CO value $\leq 2.0\%$ FCOHb.
- Subject has a physical status of ASA I or II (American Society of Anesthesiology Class 1; Healthy subjects without any systemic disease at all. American Society of Anesthesiology Class II; subjects with mild systemic disease) as it applies to the systemic disease portion of the classification.
- Blood Pressure: (Systolic BP ≤ 140 mmHg and ≥ 90 mmHg, Diastolic BP ≤ 90 mmHg and ≥ 50 mmHg), and if blood pressure is lower than 100/60 subject passes an orthostatic blood pressure test
- Subject is able to read and communicate in English and understands the study and risks involved.

Oxygen Reserve Index (ORi) Expanded Data Set Validation of INVSENSOR00025

5.2. Exclusion Criteria (*= Per physician discretion)

- Subject is pregnant.
- Subject has a BMI > 35 and has been classified as morbidly obese or at an increased risk for participation by a medical professional.
- Subject has a history of fainting (vasovagal), blacking out or losing consciousness during or after a blood draw, or has a fear of blood draws.
- Subject smokes one pack of cigarettes or more in one week, and/or the equivalent of e-cigarette liquid, and smokers are not being recruited as indicated in the CSRF.
- Subject has open wounds, inflamed tattoos or piercings and/or any visible healing wounds that a medical professional renders them at an increased risk for participation.*
- Subject has known drug or alcohol abuse or uses recreational drugs.
- Subject experiences frequent or severe headaches and/or migraine headaches, migraine auras, altitude sickness, and/or headaches accompanied by visual changes or sensitivity to light or sound.
- Subject has experienced a concussion or head injury with loss of consciousness within the past 12 months.
- Subject has any history of a stroke, myocardial infarction, seizures or heart attack.
- Subject who has taken anticoagulant medications within the last 30 days (excluding nonsteroidal anti-inflammatory drugs (NSAIDS).
- Subject has donated blood within the past 4 weeks.
- Subject has any chronic bleeding disorder (i.e. hemophilia)
- Subject has any symptomatic cardiac dysrhythmia (i.e. atrial fibrillation) and has not received clearance from their physician to participate.
- Subject has Wolff-Parkinson-White Syndrome or Stokes - Adams syndrome.
- Subject has known neurological and/or psychiatric disorder (i.e. schizophrenia, bipolar disorder, Multiple Sclerosis, Huntington's disease) that interferes with the subjects' level of consciousness.
- Subject has taken opioid pain medication within 24 hours of start of study.
- Subject has any type of infectious disease (i.e. Hepatitis, HIV, Tuberculosis, Flu, Malaria, Measles, etc.).
- Subject is taking medications known to treat any type of infectious disease.*
- Subject has either signs or history of peripheral ischemia or carpal tunnel syndrome.
- Subject has had invasive surgery within the past year- including but not limited to major dental surgery*, appendix*, plastic surgery*.
- Subject has had invasive surgery within the past year- including but not limited to gallbladder, major fracture repairs (involving plates/ screws), jaw surgery, urinary tract surgery, major ENT surgery, joint replacement or gynecological surgeries, heart surgery or thoracic surgery.
- Subject has symptoms of congestion, head cold, flu or other illnesses.
- Subject is claustrophobic and/or has generalized anxiety disorder.
- Subject has been in severe car accident(s) or a similar type of accident(s) requiring hospitalization within the past 12 months.
- Subject has any cancer or history of cancer (not including skin cancer).*
- Subject has chronic unresolved asthma, lung disease (including COPD) and/or respiratory disease.
- Subject is allergic to lidocaine, latex, adhesives, or plastic.
- Subject has a heart condition, insulin-dependent Diabetes, or uncontrolled hypertension.
- Subject has delivered vaginally, has had a pregnancy terminated, a miscarriage with hospitalization, or had a C-section within the past 6 months.

Oxygen Reserve Index (ORi) Expanded Data Set Validation of INVSENSOR00025

- Subject intends to participate in any heavy lifting, repetitive movement of their wrist (including riding a motorcycle, tennis) or exercise (working out, riding a bike, riding a skate board etc.), or any activity that will put additional stress on the wrist within 24 hours following a study that involved an arterial line.
- Subject has any medical condition which in the judgement of the investigator and/or medical staff, renders them ineligible for participation in this study (Discretion of investigator/study staff).

5.3. **Withdrawal of subjects**

Subjects must be withdrawn under the following circumstances:

5.3.1 The subject withdraws consent.

5.3.2 Discretion of investigator, for example:

- The investigator feels that the subject is too money motivated.
- The investigator feels that the subject does not fully comprehend and understand the consent form.
- The subject is ill-mannered and/or shows aggressive behavior towards study staff.
- Malfunction of the device for greater than 30 minutes that prevents accurate collection of optical data.
- Subject displays or communicates signs of discomfort or distress so that the study may not be continued.

5.4. **Replacement of subjects**

In case a subject is withdrawn from the study, another subject may be recruited.

6. **EQUIPMENT AND MATERIALS**

Equipment and Materials: All lab analyzers and equipment will be maintained per manufacturer specifications and all study personnel will be trained on the use of relevant equipment. Equivalent equipment and materials to those listed below may be used.

Safety Equipment (FDA-Cleared)

- Blood pressure monitoring system
- Electrocardiogram (ECG)
- Masimo Pulse Oximeters (Radical-7) - for subject safety monitoring
- Pulse oximeter sensors and cables (Masimo SET, Masimo rainbow)
- Masimo Patient Monitoring Platform (Root®)- for subject safety monitoring
- Medical-grade Oxygen tank and mask
- Crash cart

Test Devices

- Masimo INVSENSOR00025 sensor – Investigational
- Masimo Patient Monitoring Platform (Root®)
- Masimo Pulse Oximeters (Radical-7)

Oxygen Reserve Index (ORi) Expanded Data Set Validation of INVSENSOR00025

Research Equipment

- Laboratory co-oximeters/blood analyzers

7. PROCEDURE

7.1 SCHEDULE OF ACTIVITIES

[illegible]

Oxygen Reserve Index (ORi) Expanded Data Set Validation of INVSENSOR00025

7.2. RECRUITMENT AND PRESCREENING

Subjects will be recruited using IRB-approved advertisements. Subjects may be referred to the study by previous subjects. Subjects are contacted via phone call to conduct a prescreening interview to determine their initial eligibility for the study. Potential eligible subjects are scheduled for a study visit to the clinical laboratory.

7.3. CONSENTING AND SCREENING

Study staff will discuss the informed consent process and the study with the potential subjects. The subjects will be provided with enough time to read and understand the informed consent document and their questions will be answered by study staff prior to the subject signing the informed consent form. No study related activities will be conducted until consent is signed.

Subjects will be asked to provide a copy of their valid government photo ID and/or Social Security Number (SSN) card to verify subject identity. The copies of these forms of identification will be stored along with the subject's consent. The confidentiality and retention of these documents will be protected to the extent provided and required by law.

Subjects will be asked a brief series of health questions to ensure their eligibility for this study. Subjects who do not meet the inclusion and exclusion criteria will not be eligible to participate in the study.

[REDACTED]

In addition, a medical history will be recorded after the initial screening questionnaire.

Pre-procedure vital signs will be recorded for subject safety monitoring. Spikes in blood pressure and heart rate can be expected during line placement, needle sticks, blood draws etc. and may also be attributed to anxiety/nervousness relating to a new environment. Only the initial recorded blood pressure and/or heart rate determines a subject's qualification for the study.

A physician will perform an orthostatic blood pressure test on subjects with an initial blood pressure [REDACTED]. The orthostatic blood pressure test will start with the physician taking the subject's blood pressure while they are lying in supine position. The subject will then stand up for 30 seconds and a second blood pressure measurement will be taken. The subject's blood pressure will need to stay [REDACTED] to meet inclusion criteria for the study.

Female subjects will be required to take a pregnancy test. Results will be noted in study documentation. If the pregnancy test is positive, the subject will be notified and removed from the study.

[REDACTED]

Subjects may have a blanket placed on them for their comfort.

Subjects may be offered a snack (e.g., granola bar) and/or beverage (e.g., water, juice) due to the amount of time their involvement in this study may take.

Oxygen Reserve Index (ORi) Expanded Data Set
Validation of INVSENSOR00025

7.4. PROCEDURES

If accepted into the study, standard hospital-type monitors will be placed on the subject, including ECG, blood pressure, and a reference pulse oximeter for safety monitoring by medical staff.

[REDACTED]

[REDACTED]

Local anesthetics such as lidocaine, ethyl chloride spray, or Pain Ease skin refrigerant spray may be used in the event that an IV is placed to numb the site. Subjects will be given the option to have lidocaine or numbing spray be used during IV placement for the purpose of making catheter placement more comfortable for the subjects.

[REDACTED]

[REDACTED], sensors will be placed on the required sensor sites.

[REDACTED]

[REDACTED]

[REDACTED]

The timing of all the blood draws will be entered into the data collection software.

If at any point the subject is uncomfortable with the study, the study will be stopped.

[REDACTED]

7.5. END OF STUDY PROCEDURE

At the conclusion of the procedure, the sensors/devices, IV(s), [REDACTED] will be removed and the subject will be allowed to leave after medical personnel determine it is safe to do so.

Study staff may take [REDACTED] to verify the subjects blood values are within normal range (eg. pH, Glucose, etc.)

The total procedure time will be approximately [REDACTED].

**Oxygen Reserve Index (ORi) Expanded Data Set
Validation of INVSENSOR00025**

All subjects will be encouraged to remain in the study area until they feel fit to leave; subjects should feel safe and able before returning to work directly after participation in the study.

Subjects will be given instructions on wound care. All subjects will be instructed to contact the principal investigator or study staff in the event of any potential complication.

Subjects will be paid for their time.

After the study has ended subjects will be offered a snack (e.g., Granola bar) and something to drink (e.g., water or juice). Subjects are asked to consume food and/or liquid prior to leaving the clinical lab area for their safety due to study procedures such as blood removal. Subjects may also be asked to wait in the clinical lab or lobby waiting area for an additional 30 minutes (estimate) before leaving to allow for their body to continue adjusting after the study has completed.

7.6. RE-CONTACTING SUBJECTS

If the subject fails to provide proper documentation on their individual consent form for any study, Masimo has the right to re-contact the subject and ask them to return to the clinical lab in order to properly complete the consent form or subject bill of rights. Subject will be compensated for travel.

The subject will also fill out other study documents. These documents aid in the collection of data, tracking subject count, etc. If the subject fails to provide proper documentation on other documents, Masimo has the right to re-contact the subject and ask them to return to the clinical lab in order to properly complete these documents if seen as necessary by study staff.

The subject will be re-contacted via phone or email and be asked to return as soon as possible.

8. ACCEPTANCE CRITERIA (JUSTIFY IF NOT APPLICABLE)

[REDACTED]

9. SAMPLE SIZE JUSTIFICATION

[REDACTED]

10. DATA ANALYSIS PROCEDURE TO BE USED

EXCLUSION CRITERIA FOR DATA ANALYSIS

In order to ensure the validity of the measurements, each ORI/PaO2 data pair was evaluated through the following criteria to remove samples that could be erroneous due to various reasons such as Reference Errors, User Errors, or ORI monitoring system Quality Checks as listed below

1. Reference Errors: Samples reported with an exception (e.g., "Error Codes from reference machine") from reference machine are discarded for data analysis, since the PaO2 measurement may not be reliable or will not be available.
2. ORI monitoring system error: Samples reported with ORI system exception [REDACTED] are discarded for data analysis, since the ORI value may not be available or reliable.
3. Incomplete study: Data from subjects who did not go through the full protocol are excluded from data analysis

Oxygen Reserve Index (ORi) Expanded Data Set Validation of INVSENSOR00025

4. For a given FiO2 level, each of the [REDACTED] PaO2 blood draws that are sampled [REDACTED] apart are discarded, since the sampling time difference may result in the data [REDACTED] not being reflective of one another resulting in the erroneous inclusion of the PaO2 reference for data analysis. Also [REDACTED] PaO2 blood draws with values with differences [REDACTED] are discarded for data analysis, as the difference may be reflective of an erroneous or inconsistent PaO2 reference.
5. Exclusion Criteria for PaO2 levels outside ORi sensitive region (100 to 200 mmHg)
 - a. PaO2 values below 100 mmHg and above 200 mmHg are discarded for data analysis, as the focus of the study is the validation of ORi in the moderate hyperoxic range (of 100 to 200 mmHg PaO2).
6. Samples with $|\Delta\text{PaO}_2|$ [REDACTED] or $|\Delta\text{ORi}|$ [REDACTED] are excluded for data analysis of the sensitivity, specificity or concordance computation, since these changes are not considered significant reflections of changes in oxygen status based upon the repeatability and reproducibility analysis described below.

ΔPaO_2 and ΔORi were computed by taking the difference of all ORi and PaO2 readings from the study with this chosen PaO2 threshold level.

ΔPaO_2 and ΔORi computation are defined as:

$$\Delta\text{PaO}_2 = \text{PaO}_2(t) - \text{PaO}_2(t_{\text{ref}})$$

$$\Delta\text{ORi} = \text{ORi}(t) - \text{ORi}(t_{\text{ref}})$$

where 'tref' is the time of the sample closest to PaO2threshold in a [REDACTED] window

't' represents all other time synchronized ORi/PaO2 data pair from the study

[REDACTED]

Specificity, sensitivity and concordance will be computed for changes in ORi with respect to changes in PaO2 as described below:

ΔPaO_2 vs ΔORi

ΔPaO_2 and ΔORi are defined below.

$$\Delta\text{PaO}_2 = \text{PaO}_2(t) - \text{PaO}_2(t_{\text{ref}})$$

where t_{ref} is the time of the sample closest to $\text{PaO}_{2\text{threshold}}$ in a [REDACTED] (see footnote*) window. A [REDACTED] window is used as it is not possible to draw a blood sample at the exact desired value of $\text{PaO}_{2\text{threshold}}$. PaO_2 can be any value from 110 to 190 in steps of 10mmHg (see footnote) to cover the range of 100 to 200mmHg..

$$\Delta\text{ORi} = \text{ORi}(t) - \text{ORi}(t_{\text{ref}})$$

Samples with ΔPaO_2 of [REDACTED] are ignored (see footnote*).

Oxygen Reserve Index (ORi) Expanded Data Set
Validation of INVSENSOR00025

- 1) As per Figure 2, specificity is defined as
Specificity = $N1 / (N1 + N4)$
- 2) As per Figure 2, sensitivity is defined as
Sensitivity = $N3 / (N2 + N3)$
- 3) As per Figure 2, concordance is defined as
Concordance = $(N1 + N3) / (N1 + N2 + N3 + N4)$

The relationship between Concordance, Specificity and Sensitivity is as shown below.

Let $N = (N1 + N2 + N3 + N4)$

$$\begin{aligned} \text{Concordance} &= \frac{N1}{N} + \frac{N3}{N} \\ &= \frac{N1 (N1+N4)}{N (N1+N4)} + \frac{N3 (N2+N3)}{N (N2+N3)} \\ &= \frac{N1+N4}{N} * \text{Specificity} + \frac{N2+N3}{N} * \text{Sensitivity} \end{aligned}$$

$$\text{Concordance} = \alpha * \text{Specificity} + (1 - \alpha) * \text{Sensitivity}$$

where $0 \leq \alpha \leq 1$.

[figure not shown]

Figure 2: Specificity and Sensitivity Illustration for ΔPaO_2 vs ΔORi

⁵ Bedford, Robert F. MD, (1978), Long-term radial artery cannulation: effects on subsequent vessel function, *Critical Care Medicine*, 6 (1), 1-71.

⁵ Slogoff S, Keats AS, Arlund C, (1983), On the safety of radial artery cannulation, *Anesthesiology*, 59 (1), 42-47.

Oxygen Reserve Index (ORi) Expanded Data Set Validation of INVSENSOR00025

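### Exclusion criterion 6 drops pairs because ORi changed little, even where PaO2 clearly changed, so sensitivity and directional concordance describe only pairs in which ORi responded

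*Combined protocol and SAP*

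**What the plan says.** Section 1 (Outcome Measure) names two results: ORi sensitivity, and concordance of the direction of ORi changes with that of PaO2 changes between 100 and 200 mmHg.

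Section 10 lists six exclusions before these are computed. Criterion 6 has two arms. The first concerns |ΔPaO2|. The second concerns |ΔORi|, and samples that meet either arm "are excluded for data analysis of the sensitivity, specificity or concordance computation, since these changes are not considered significant reflections". The stated reason in full is "since these changes are not considered significant reflections of changes in oxygen status based upon the repeatability and reproducibility analysis described below". Both cuts and their comparison signs are redacted, but the reason shows that small changes are the ones removed. Because the arms are joined by *or*, a small |ΔORi| alone is enough to remove a pair.

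The later part of Section 10 (ΔPaO2 vs ΔORi) states, as far as it can be read, "Samples with ΔPaO_2 of [REDACTED] are ignored (see footnote" and points to a footnote that is not visible. It then defines specificity as N1/(N1+N4), sensitivity as N3/(N2+N3) and concordance as (N1+N3)/(N1+N2+N3+N4), with cells taken from Figure 2. These formulas have no cell for a pair in which PaO2 changed and ORi did not.

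**The concern.** Filtering on the reference is sound: the |ΔPaO2| limit decides when a real change took place. Filtering on the index test's own result is different. When PaO2 has moved beyond its limit and ORi has stayed near flat, the device has not shown a change that the reference confirms. Criterion 6 takes that pair out of both numerator and denominator.

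The exclusion list is introduced as a way to remove possibly erroneous samples. Criteria 1, 2 and 4 already cover reference errors, ORi system exceptions and inconsistent blood draws, so the ORi arm also reaches pairs that passed all of those checks. A repeatability argument can support calling such a pair a non-response. It does not support dropping the pair when the reference clearly changed.

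At stake is what the outcome measures mean. Section 2.2 uses concordance to validate that ORi can monitor oxygenation status in moderate hyperoxia. A figure conditional on ORi having moved supports a narrower claim.

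**Working it through.** **Inputs.** From Section 10: the *or* in criterion 6, its repeatability reason and the three formulas. From Section 1: the outcome measures. Acceptance criteria (Section 8) and sample size (Section 9) are redacted, so there is no planned figure to reproduce. The quantities p, m and q below are assumptions.

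**Step 1: formulas.** The plan's identity, concordance = α × specificity + (1 − α) × sensitivity, holds. With N1 = 40, N2 = 5, N3 = 50, N4 = 5: α = 45/100, and 0.45 × 40/45 + 0.55 × 50/55 = 0.40 + 0.50 = 0.90 = (40 + 50)/100.

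**Step 2: algebra.** Among pairs with a qualifying |ΔPaO2|, let m be the share dropped only for a small |ΔORi|, p the agreement among retained pairs, and q the share of dropped pairs whose sign is right.

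- Criterion 6 reports p.
- Detection rate (non-response counted as a miss): p(1 − m), below p whenever m > 0 and p > 0.
- Sign scoring of all qualifying pairs: p(1 − m) + qm. The reported value exceeds this by m(p − q), which is positive only if q < p.

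For sensitivity, m, p and q refer to the pairs in N2 + N3 and those dropped from that direction of change.

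**Step 3: numbers for p = 95%.**

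| m | Detection rate | By sign, q = 0.6 | By sign, q = 0.5 |
|---|---|---|---|
| 5% | 90.25% | 93.25% | 92.75% |
| 10% | 85.5% | 91.5% | 90.5% |
| 20% | 76.0% | 88.0% | 86.0% |
| 30% | 66.5% | 84.5% | 81.5% |

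For example, at m = 10% and q = 0.6: 0.95 × 0.90 + 0.6 × 0.10 = 0.855 + 0.060 = 0.915.

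**Step 4: simulation, all settings assumed.** PaO2 was uniform on 100 to 200 mmHg and the reference sample uniform on 110 to 190. A qualifying change was |ΔPaO2| ≥ 10 mmHg. ΔORi was 0.005 per mmHg plus normal noise (SD 0.05, 0.10 or 0.15), and the ORi cut was 0.02, 0.05 or 0.10, giving nine settings. Concordance in three of them:

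| Noise SD | ORi cut | Dropped | Criterion 6 | By sign, all pairs | Non-response as miss |
|---|---|---|---|---|---|
| 0.05 | 0.02 | 3.0% | 99.1% | 98.0% | 96.1% |
| 0.10 | 0.05 | 13.1% | 95.8% | 91.5% | 83.2% |
| 0.15 | 0.10 | 27.3% | 92.8% | 84.9% | 67.5% |

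The middle row agrees with the algebra: 0.958 × (1 − 0.131) = 0.8325. It implies q = (0.915 − 0.832)/0.131 = 0.63, well below p. Across the nine settings, 3% to 27% of qualifying pairs were dropped. Concordance under criterion 6 was higher by about 1 to 8 points than sign scoring (99.1 − 98.0 = 1.1 up to 92.8 − 84.9 = 7.9). It was higher by about 3 to 27 points than counting non-response as a miss.

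**Step 5: specificity.** If Figure 2 defines specificity as ORi not rising when PaO2 falls, a flat ORi is a true negative. Restoring D such pairs gives (N1 + D)/(N1 + N4 + D), which is at least N1/(N1 + N4). In the middle setting specificity would then be 0.963, against 0.958 under criterion 6. Sensitivity in that setting falls from 0.958 to 0.831 with non-response as a miss. With rises and falls about equal in number, as the simulated design makes them, concordance on this reading is (0.831 + 0.963)/2 = 0.897, still below 0.958.

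**The case against.** The strongest reply is that ORi is presented as a directional trending index. Agreement in direction, given that both measures moved beyond repeatability, is a coherent quantity; a detection rate is a different one, and the gap between them need not be called bias. Part of this stands. The present figure can be reported, provided that it is labelled as conditional on an ORi response. It also means that scoring every small ΔORi as a miss should not be the only scoring, because that penalises small changes in the correct direction. What does not follow is that the conditional figure can serve alone as evidence of how often ORi reflects a real PaO2 change.

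The reply also points to redactions. The repeatability analysis, the footnote, the acceptance limit and the sample-size basis cannot be read; they may justify the ORi cut, or provide for a count of dropped pairs. That is so, and no omission is alleged there. But a rationale for the size of the cut would not change which pairs it removes. If the cut is very small, m may be negligible.

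A reader might infer three stronger points that the documents do not support:

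- That all three measures are inflated. Figure 2 is not shown, and on one reading specificity would be lowered (Step 5).
- That Section 10 contradicts itself because its later description visibly names only ΔPaO2. That sentence contains a redaction and refers to an unseen footnote, either of which could cover ΔORi.
- That this sensor often stays flat and would still score near 100%. Nothing readable shows how often ORi fails to respond.

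**Conclusion.** The point holds for sensitivity and directional concordance. Criterion 6 removes pairs on the index test's own result, so both measures are computed only where ORi responded. As statements of how often ORi reflects a real PaO2 change, they are too high by pm on the detection scale whenever any such pair is dropped (m > 0). On the sign scale the excess is m(p − q). It is expected, because agreement should be weaker when ΔORi is near zero, but it is not certain.

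The size cannot be found from the documents. The 1 to 8 points (by sign) and 3 to 27 points (non-response as a miss) rest on the assumed slope, noise and cuts, and illustrate the mechanism only. The reading that small changes are the ones removed rests on the stated reason, since the comparison signs are redacted. No conclusion is drawn for specificity, or about consistency between the two descriptions in Section 10.

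**What to change.** In Section 10:

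1. For the primary analysis, apply the exclusion zone to |ΔPaO2| only. Keep every pair with a qualifying |ΔPaO2| that passes the other criteria, classify it by the sign of ΔORi, and count zero change as not concordant.
2. Report the number of pairs with |ΔORi| below its cut as a separate no-response count, for rises and for falls in PaO2.
3. Add a sensitivity analysis that scores those pairs as not detected.
4. Keep the present double-exclusion result as a secondary analysis, labelled as conditional on an ORi response, with the number of pairs that it removes.

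The cost is a short text change and a recount of pairs that the study collects anyway, with no added subjects or blood draws for the recount itself. Reported sensitivity and concordance will probably be less favourable. Any acceptance limit in Section 8, or sample-size basis in Section 9, that was set under the double exclusion must be checked against the new definition.
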